15.1 Definitions

Device Deficiency

Inadequacy of a medical device with respect to its identity, quality, durability, reliability, usability, safety or performance. Device deficiencies include malfunctions, use errors and inadequacy in the information supplied by the manufacturer, including labelling.

This definition includes device deficiencies related to the investigational medical device or the comparator.

Adverse Event (AE)

An AE is any untoward medical occurrence, unintended disease or injury, or untoward clinical signs (including abnormal laboratory findings) in subjects, users or other persons, whether or not related to the investigational medical device and whether anticipated or unanticipated.

Adverse Device Effect (ADE)

Any AE related to the use of the investigational medical device.

This definition includes adverse events resulting from insufficient or inadequate instructions for use, deployment, implantation, installation, or operation, or any malfunction of the investigational medical device.

This definition includes any event resulting from use error or from intentional misuse of the investigational medical device.

This includes "comparator" if the comparator is a medical device.

Serious Adverse Event (SAE)

An AE that led to any of the following:

- a) Death,
- b) Serious deterioration in the health of the subject, users or other persons as defined by one or more of the following:
 - 1) a life-threatening illness or injury, or
 - 2) a permanent impairment of a body structure or a body function including chronic diseases, or
 - 3) in-patient or prolonged hospitalization, or
 - 4) medical or surgical intervention to prevent life-threatening illness or injury, or permanent impairment to a body structure or a body function,
- c) Foetal distress, foetal death, a congenital abnormality, or birth defect including physical or mental impairment

Planned hospitalization for a pre-existing condition, or a procedure required by the CIP, without serious deterioration in health, is not considered a serious adverse event.

Serious adverse device effect (SADE)

Adverse device effect that has resulted in any of the consequences characteristic of a serious adverse event.

Unanticipated Serious Device Effect (USADE)

Serious adverse device effect which by its nature, incidence, severity or outcome has not been identified in the current risk assessment.

Anticipated serious adverse device effects (ASADE) is an effect which by its nature, incidence, severity or outcome has been identified in the risk assessment.

15.2 Classification of an Adverse Event

15.2.1 Severity of Event

For all AEs, the following guidelines will be used to describe severity:

- **Mild** Events require minimal or no treatment and do not interfere with the participant's daily activities.
- Moderate Events result in a low level of inconvenience or concern with the therapeutic measures. Moderate events may cause some interference with functioning.
- Severe Events interrupt a participant's usual daily activity and may require systemic drug therapy or other treatment. Severe events are usually potentially life-threatening or incapacitating. Of note, the term "severe" does not necessarily equate to "serious".

15.2.2 Causality assessment

All AEs must have their relationship to both the study device and study procedure assessed and categorized by the Principal Investigator who examines and evaluates the participant based on the temporal and/or biological relationship and his/her clinical judgment. During assessment, relevant core documents (e.g. CIP, IB and RM report) must be consulted. The Sponsor and the investigators will use the following definitions to assess the relationship of the serious adverse event to the investigational device, sham or the investigation procedure.

Not related: Relationship to the device, sham or procedures can be excluded when:

- the event has no temporal relationship with the use of the investigational device, or the procedures related to application of the investigational device;
- the serious adverse event does not follow a known response pattern to the medical device (if the response pattern is previously known) and is biologically implausible;
- the discontinuation of medical device application or the reduction of the level of activation/exposure - when clinically feasible - and reintroduction of its use (or increase of the level of activation/exposure), do not impact on the serious adverse event;
- the event involves a body-site or an organ that cannot be affected by the device or procedure;
- the serious adverse event can be attributed to another cause (e.g. an underlying or concurrent illness/ clinical condition, an effect of another device, drug, treatment or other risk factors);
- the event does not depend on a false result given by the investigational device used for diagnosis, when applicable;
- **Possible:** The relationship with the use of the investigational device or comparator, or the relationship with procedures, is weak but cannot be ruled out completely.

Alternative causes are also possible (e.g. an underlying or concurrent illness/ clinical condition or/and an effect of another device, drug or treatment). Cases where relatedness cannot be assessed, or no information has been obtained should also be classified as possible.

Probable: The relationship with the use of the investigational device or comparator, or the relationship with procedures, seems relevant and/or the event cannot be reasonably explained by another cause.

Causal The serious adverse event is associated with the investigational device, comparator **relationship:** or with procedures beyond reasonable doubt when:

- the event is a known side effect of the product category the device belongs to or of similar devices and procedures;
- the event has a temporal relationship with investigational device use/application or procedures;
- the event involves a body-site or organ that
 - the investigational device or procedures are applied to;
 - the investigational device or procedures have an effect on;
- the serious adverse event follows a known response pattern to the medical device (if the response pattern is previously known);
- the discontinuation of medical device application (or reduction of the level of activation/exposure) and reintroduction of its use (or increase of the level of activation/exposure), impact on the serious adverse event (when clinically feasible);
- other possible causes (e.g. an underlying or concurrent illness/ clinical condition or/and an effect of another device, drug or treatment) have been adequately ruled out;
- harm to the subject is due to error in use;
- the event depends on a false result given by the investigational device used for diagnosis, when applicable;

15.2.3 Expectedness

Expected events have been identified from vigilance data, available clinical data and literature searches. Investigator will use available technical documentation to determine if the event is anticipated or not. An AE will be considered unexpected if the nature, severity, or frequency of the event is not consistent with the risk information previously described for the study intervention.

15.3 Adverse event recording

The Investigator will monitor the occurrence of adverse events for each subject during the course of the clinical study. Adverse events (AEs) may be reported by the participant, identified by the PI or documented in the medical record. All AEs regardless of source, must be recorded in the EDC system. Throughout the study, participants must immediately report any adverse events and device deficiencies experienced through the ePRO, which will be recorded by investigators in the electronic Case Report Form (eCRF). The Investigator must provide information on symptoms, date and time of onset, duration, severity, seriousness rating, causality, actions taken, outcome and any other pertinent information. All AEs occurring while in study must be documented appropriately regardless of relationship. All AEs will be followed to adequate resolution. Any medical condition that is present

at the time of screening will be considered as baseline and not reported as an AE. However, if the study participant's condition deteriorates at any time during the study, it may be recorded as an AE.

Changes in the severity of an AE will be documented to allow an assessment of the duration of the event at each level of severity to be performed.

A hard copy of the electronic AE section will be available to allow the Investigator to report SAEs and device deficiencies in the event the EDC is not available. The AE report must then be sent to: [contact]

Detailed instruction on reporting and completion of the AE section will be provided to the sites as part of the Site Initiation Visit (SIV).

15.4 Adverse Event Reporting by Investigators

If any event is considered (possibly) related to the device, event is considered serious or event is device deficiency with SAE potential, it is the responsibility of the Investigator to report this event within **24 hours** of awareness. If event is not serious or not related to the device, the Investigator must complete recording in EDC within 7 days of having become aware of the adverse event.

Overview of all (S)AEs will be provided to involved ECs in annual reports.

15.5 Adverse Event Reporting by Sponsor

The safety monitoring and documentation by Sponsor as well as reporting of events and device deficiencies to involved regulatory authorities is described in the Safety Management Plan for the study. Sponsor's Medical Advisor for study will review clinical events that occur during the study to adjudicate the relationship to the study device and safety, seriousness, severity and expectedness. Sponsor will together with Medical Advisor be responsible for monitoring the safety of study participants throughout the study on an on-going basis. Based on safety data, the Medical Advisor may recommend the Sponsor to modify or stop the clinical investigation. All relevant documentation for safety review will be filed in the TMF.

The Medical Advisor for study has no involvement in the design of the clinical study and no financial interest in the investigational study product and is not involved in the conduct of the study except for his/her role as Medical Advisor and for being part of Sponsor's advisory board.

No Data Monitoring Committee will be established for this study.

This plan will be updated throughout the duration of the study if new information and/or guidance become available. Adverse events and device deficiencies will be collected and documented and reported according to applicable regulation (EU, MDCG 2020-10; US: §812.150(b)(1). In addition to the reporting requirements outlined above, national requirements, will be followed. Once Eudamed becomes available and fully functional, the Safety plan will be updated to reflect the new web-based reporting structure.

15.6 Monitoring and Follow up

Study site will record all events and will monitor those throughout the study until 7 (for non-serious AEs) or 30 days (for SAEs) after the last day of study participation.

16 Methods for analyzing data

The **PAREMA1 Statistical Analysis Plan** (SAP) describes the statistical method and analysis in detail. Following is a summary of the intended analyses and sample size justification.

16.1 Primary Effectiveness Analysis

The primary endpoint is Absence of Moderate or Severe pain at 2 hours (AMSP2), i.e. the percentage of study attacks in which the participant reported absence of headache of moderate/severe intensity at 2 hours post-treatment initiation. "Study attacks" are all attacks treated and reported during Stage 1, apart from the first attack which is a training attack and is not included in the analysis. The intention-to-treat (ITT) analysis set will be used for the primary effectiveness hypothesis test. The primary effectiveness hypothesis is:

H₀: $p_{Rehaler} = p_{sham}$ H_a: $p_{Rehaler} \neq p_{sham}$ Where: $p_{Rehaler} = proportion of attacks in the Rehaler group with AMSP2$ $p_{sham} = proportion of attacks in the sham group with AMSP2$

The primary effectiveness hypothesis will be tested using a two-sided adjusted χ^2 test for clustered binary data (Donner and Banting, 1988), at a 5% level of significance. If Pearson's chi-squared test statistic is written as $\chi^2 = \sum_{i=1}^{G} \chi_i^2$ with G = the number of treatment groups, then the adjusted χ^2 approximately follows a chi-squared distribution with G-1 degrees of freedom and is calculated as follows (Donner and Banting, 1988):

$$\chi_A^2 = \sum_{i=1}^G \frac{\chi_i^2}{\overline{C}_i}$$

Where:

$$\overline{C}_{i} = \sum_{j=1}^{n_{i}} \frac{m_{ij}C_{ij}}{\sum m_{ij}}$$

 $C_{ij} = 1 + (m_{ij} - 1)\rho$

G is the number of treatment groups

 $n_{i}\xspace$ is the number of individuals in group j

 $\boldsymbol{\rho}$ is the correlation coefficient between any two responses in the same individual

m_{ij} denotes the number of observations for individual j in group i

The corresponding 95% confidence interval for the difference in proportion of attacks with AMSP2 between the Rehaler and sham groups will be calculated as follows (Donner and Klar, 1993):

95% Confidence Interval: $(\hat{p}_{Rehaler} - \hat{p}_{sham}) \pm 1.96 * \widehat{SE}(\hat{p}_{Rehaler} - \hat{p}_{sham})$

Where:

 $\hat{p}_{Rehaler}$ = observed proportion of attacks in the Rehaler group with AMSP2

 \hat{p}_{sham} = observed proportion of attacks in the sham group with AMSP2

$$\begin{split} \widehat{SE}(\hat{p}_{Rehaler} - \hat{p}_{sham}) &= \left(\frac{\overline{C_1}\hat{p}_{Rehaler}(1 - \hat{p}_{Rehaler})}{n_1} + \frac{\overline{C_2}\hat{p}_{sham}(1 - \hat{p}_{sham})}{n_2}\right)^{1/2} \\ \overline{C}_l &= \sum_{j=1}^{n_l} \frac{m_{ij}C_{ij}}{\sum m_{ij}} \\ C_{ij} &= 1 + (m_{ij} - 1)\rho \end{split}$$

n_i is the number of individuals in group i

 ρ is the correlation coefficient between any two responses in the same individual m_{ij} denotes the number of observations for individual j in group i

16.2 Sample Size and Statistical Power

The study's key secondary endpoint is Pain Freedom at 2 hours (PF2). Recognizing that this is the ideal outcome for migraine patients, the study has been designed with a moderately high statistical power (80%) for PF2. The estimated study size of 174 included participants has been determined on the basis of data from the pilot study and post-market data collected in Denmark, Sweden and Germany from 2018 to 2020, indicating that the PF2 rate will be 30% in the active device group and 12% in the sham group, that each patient will contribute data from two attacks while in Stage 1, and that the total percentage of included patients not yielding analyzable data will be 30%. These data were utilized in a sample size analysis, conducted by simulation and using the χ^2 significance test adjusted for clustered data. Under the given assumptions and including 174 patients, the estimated power for PF2 is 80%. Pilot study and post-market data indicated an AMSP2 rate of 61% in the study will result in 95% power for AMSP2. Therefore, the clinical investigation will randomize at minimum 174 participants.

16.3 Interim analysis

After 60 subjects have provided data from at least one study attack in Stage 1, an interim analysis (IA) will be conducted to re-estimate the study sample size. Based on the data from the IA it will be decided how many additional patients to recruit into the study. The IA will include two hypothesis tests on the interim data set, respectively of PF2 and AMSP2. These analyses will use the O'Brien Fleming Spending function in which the significance thresholds of the p-value are respectively 0.0052 at the IA and 0.048 in the full analysis. The IA will estimate the power for PF2 in the final analysis based on the observed PF2 rates in the trial thus far and re-estimate the study sample size accordingly. Regardless of the results of the IA, enrolment will continue to the originally estimated 174 subjects, and the total number of included participants will be capped at 220 since this is the largest study that will be feasible to conduct. The minimum number of participants in the study will be 174.

16.4 Analysis of Secondary Effectiveness Endpoints

To support potential device labelling claims, key secondary end points will be analyzed according to a fixed-sequence step-down procedure. The ITT analysis set will be used for hypothesis tests for the secondary endpoints.

The end point analysis will be performed by an independent evaluator who is blinded to the type of intervention (active/sham) assigned to each of the two Stage 1 treatment groups.

16.5 Analysis of Explorative Endpoints

Explorative endpoints in Stage 1 and Stage 2 will be analyzed to gather additional effectiveness information.

16.6 Analysis of Safety Endpoints

The incidence of device- or treatment-related adverse events (AEs) and device- or treatment-related serious adverse events (SAEs) and/or serious adverse device effects (SADE) will be tabulated. The astreated analysis set will be used for the assessment of safety.

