10.3.3 Blinding

To ensure optimal blinding of participants, the active and sham devices have been designed to look and feel as similar as possible (see section 8.6).

11 Endpoints

For this study to be considered successful, all primary performance and safety endpoints must be achieved. Data for all endpoints will be collected through electronic Patient Reported Outcome (ePRO). All end points have been selected with the aim of measuring effects and factors that are relevant and valuable for migraine patients.

All primary and secondary effectiveness endpoints are calculated based on data from Stage 1 of the study.

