11.2 Primary safety endpoint

- Incidence of device- or treatment-related adverse events
- Incidence of device- or treatment-related serious adverse events (SAEs) and/or serious adverse device effects (SADE)

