16.7 Pass/fail criterion to be applied to the results of the clinical investigation

The pass/fail criterion for the clinical investigation is whether using the active device per protocol results in a higher percentage of absence of moderate or severe pain at two hours compared to the sham device.

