# 1.3 Endpoints

The primary endpoint is absence of moderate or severe pain at 2 hours (AMSP2) which is an outcome that is valuable to patients and which has a good benefit risk/ratio when factoring in the low risk level of the treatment. The statistical power for AMSP2 in the study is above 95% (see section 1.5, below).

The study's most important secondary endpoint is Pain Freedom at 2 hours (PF2). Recognizing that this is the ideal outcome for patients, the study has been sized and designed with the aim of having a high statistical power for PF2.

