#### 1.6.2 As-treated analysis set

The as-treated analysis set includes all participants who received a study device, whether or not it was the actual randomized device. Subjects will be grouped by the device they actually used. This analysis set will be used for assessment of safety.

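### The only planned safety table is limited to events rated device- or treatment-related, so neither document shows all Stage 1 adverse events by arm

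*Protocol*

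**What the plan says.** Protocol section 11.2 defines the primary safety endpoint in two items. The first is "Incidence of device- or treatment-related adverse events"; the second is the corresponding incidence of related SAEs and/or serious adverse device effects. Section 16.6 turns these into the analysis: "The incidence of device- or treatment-related adverse events (AEs) and device- or treatment-related serious adverse events (SAEs", with serious adverse device effects, are to be tabulated on the as-treated set. That set groups participants by the device they actually used (16.8.2), which is where the split by arm comes from.

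The opening of Protocol section 16 sends the reader to the SAP for detail: "SAP) describes the statistical method and analysis in detail. Following is a summary of the intended analyses and sample size justification". On safety the SAP is nearly silent. Section 1.3 begins "The primary endpoint is absence of moderate or severe pain at 2 hours (AMSP2") and discusses only effectiveness endpoints, as does section 1.7. The one safety statement is in section 1.6.2, on the as-treated set: "This analysis set will be used for assessment of safety".

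Collection is wider than analysis. Section 15.3 requires every AE to be documented whatever its relationship to the device. Section 15.4 promises ethics committees an annual overview of all AEs and SAEs, but does not describe it as split by arm. Section 19.8 promises a clinical study report without listing its safety tables.

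**The concern.** The primary objective (10.1) covers effectiveness and safety, both against sham. In a randomised, sham-controlled Stage 1, the comparison of all events by arm needs no judgement about cause, because background events should balance on average. The plan does not use this. It first asks whether each event is related to the device or treatment, and only events that pass enter the planned table.

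The setting makes attribution harder than usual. The device is used during migraine attacks, and some device effects listed in 14.1.1, such as dizziness, nausea and headache, could also be put down to the attack. At stake is whether a reader of the results could see a difference between arms in events that raters judged unrelated. As planned, no by-arm summary of those events exists, although the data will be in the database.

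**Working it through.** The documents give no adverse event rate in this trial, no safety margin and no safety hypothesis, so there is no planned figure to reproduce. The check has two parts.

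**1. What is collected and what is analysed**

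| Step | Place | Content |
|---|---|---|
| Objective | Protocol 10.1 | Safety assessed against sham |
| Recording | Protocol 15.3 | All AEs, related or not |
| Causality rating | Protocol 15.2.2 | Principal Investigator, four categories |
| Adjudication | Protocol 15.5 | Sponsor's Medical Advisor |
| Endpoint | Protocol 11.2 | Related AEs; related SAEs and/or SADEs |
| Table | Protocol 16.6 | The same two groups, as-treated set |
| SAP content | SAP 1.6.2 | Definition of the as-treated set only |
| All-event output | Protocol 15.4 | Annual ethics committee overview, not described as by arm |

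Planned by-arm summaries restricted to related events: two. Planned by-arm summaries of all events: none in either document. The Safety Management Plan was not available; section 15.5 describes it as covering safety monitoring, documentation and regulatory reporting.

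Two details are open in 16.6. It does not say whether *possible* counts as related, although 15.2.2 places doubtful cases in that category and 15.4 treats possibly related events as reportable within 24 hours. It also does not separate the stages: the opening of section 11 says "All primary and secondary effectiveness endpoints are calculated based on data from Stage 1 of the study", with no matching rule for safety, and in Stage 2 everyone uses the active device (10.3).

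**2. How informative an all-event table would be**

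This describes the proposed table. It does not measure an error in the current plan. Inputs: 100 per arm (SAP minimum 200, 1:1) or 120 per arm (SAP maximum 240), assuming all randomised participants receive a device. Assumed, not given: sham background p0 from 2% to 40%, and an active-arm excess d of 8 or 4 points. Section 14.1.1 gives only an upper bound, below 10%, for dyspnea, mild nausea and dizziness.

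Half-width of the 95% interval = 1.96 × √[p1(1 − p1)/n + p0(1 − p0)/n], with p1 = p0 + d. For p0 = 0.10, d = 0.08, n = 100: 1.96 × √(0.18 × 0.82/100 + 0.10 × 0.90/100) = 1.96 × √0.002376 = 0.096.

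The last four columns give the chance that the interval lies wholly above zero, by exact enumeration of both binomial counts.

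| Assumed p0 | Half-width, d = 8 points, n = 100 | Half-width, d = 8 points, n = 120 | d = 8, n = 100 | d = 8, n = 120 | d = 4, n = 100 | d = 4, n = 120 |
|---|---|---|---|---|---|---|
| 2% | 6.5 points | 5.9 points | 72% | 79% | 30% | 33% |
| 5% | 7.9 points | 7.2 points | 53% | 61% | 21% | 24% |
| 10% | 9.6 points | 8.7 points | 38% | 44% | 14% | 16% |
| 20% | 11.8 points | 10.8 points | 27% | 31% | 10% | 12% |
| 40% | 13.7 points | 12.5 points | 22% | 25% | 9% | 10% |

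If intervals were given for any AE and for each of the ten effects named in 14.1.1, there would be eleven. With independent intervals and no true differences, the chance that at least one excludes zero is 1 − 0.95^11 = 43%.

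**The case against.** The strongest reply is that the rating rules already catch the worrying cases. Section 15.2.2 defines *possible* as a relationship that is weak but cannot be ruled out, and names underlying illness as an alternative cause. Dizziness during use that might be migraine fits there. The *not related* criterion about another cause is worded for serious events, and the same list includes the absence of any temporal link, which dizziness during use would not meet. Known side effects count towards a causal relationship. Investigators are blinded (10.3.2, 13.7), and the Medical Advisor adjudicates (15.5). Headache and nausea at two hours are compared by arm anyway as HS2 and NS2 (11.3).

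Most of this stands. A reader might infer that device effects such as dizziness will drop out of the safety table. The documents do not support that: if *possible* counts as related, most such events are captured. A reader might also infer that the related-only table is invalid or biased in the device's favour. Blinded misattribution could shrink a real excess, but nothing shows that it will happen or by how much. Nor do unrelated events go wholly unreported: they are in the database and in the annual overview.

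The reply does not remove the remaining gap. No by-arm display exists for events rated *not related*. The protection also has soft edges: the documents do not say that the Medical Advisor is blinded, and unreported events are elicited at Site Visit 2, where allocation is disclosed. Table 4 lists the interview before disclosure, but no text requires causality to be rated first.

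**Conclusion.** The point holds as a worthwhile, low-cost improvement. The plan states a rule that selects events by causality rating, and it offers no by-arm comparison free of that rating, although randomisation supports one and the data will exist. The consequence is confined to an imbalance among events rated *not related*. Its size cannot be derived, because the documents give no share of device effects that would be rated so. The planned related-only table remains valid as far as it goes.

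This rests on the Protocol and SAP alone; a safety table specified elsewhere would answer it.

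A reader might go further and connect this to study success, since the opening of section 11 says "For this study to be considered successful, all primary performance and safety endpoints must be achieved". That step is not supported. No safety threshold is set, and section 16.7 names only the pain outcome: "The pass/fail criterion for the clinical investigation is whether using the active device per protocol" gives a higher rate of absence of moderate or severe pain than sham. Whether the trial needs a safety success criterion is a separate question, which an all-event table would not settle.

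**What to change.** In Protocol 16.6 and a short new safety paragraph in the SAP:

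1. Beside the related-only table, tabulate all Stage 1 AEs and all Stage 1 SAEs on the as-treated set, by device used and causality category, giving participants with at least one event and event counts.
2. State that *possible* or stronger counts as related.
3. Show open-label Stage 2 events separately.
4. Give a descriptive active-minus-sham risk difference with a 95% confidence interval for any AE and, optionally, for each effect listed in 14.1.1.

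Recording under 15.3 need not change. The cost is wording and a few tables from data already collected, with no new procedures and no effect on sample size or alpha. The drawback is noise: all-cause rates are higher, a modest excess would usually be missed, and several intervals will sometimes exclude zero by chance. They should therefore be labelled descriptive, and an interval that includes zero should not be read as evidence of no difference. Adding the table before the final Stage 1 unblinding would let it stand as pre-planned.
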